## 1.0 Objectives

The goals of this study are to evaluate the efficacy of JNJ-18038683 in an 8 week trial to ameliorate the cognitive deficit and reduce residual depressive symptoms in 60 stable bipolar outpatients receiving treatment for depression. JNJ-18038683 will be studied and compared with placebo as adjunctive treatment to standard pharmacologic treatment for bipolar disorder.

## 2.0 Background

#### 2.1.1 Cognitive impairment in bipolar disorder

Most, but not all, patients with bipolar disorder (BPD) have clinically significant cognitive impairment [1, 2]. Impairment is present in both the manic and depressed phases of BPD, as well as in euthymic periods [3]. The percentage of BPD patients with cognitive impairment (CIBD) varies among studies, with 40-60% representing the best estimate [3]. The weight of the evidence supports no overall difference in the type and severity of cognitive impairment in any phase of BPD, i.e. it is a stable trait feature of BPD, albeit variable from one patient to another. The most commonly affected cognitive domains are speed of processing, declarative memory, attention and working memory [3, 4]. Although CIBD is milder in severity than the cognitive impairment associated with schizophrenia (CIAS), on average, as in schizophrenia, CIBD has a major impact on function and quality of life in most patients, particularly because the greater preservation of function of BPD enables them to engage in activities which are more dependent on intact cognitive function [5]. Thus, it is highly likely that improvement in CIBD will have valuable clinical benefit, especially with regard to quality of life measures. It is reasonable to predict that treatments effective to improve CIBD could also be beneficial for CIAS. Efficacy for cognitive impairment is likely to be greater in BPD than schizophrenia, because the baseline severity is milder in the former [6]. Despite this strong rationale for targeting CIBD, there has been minimal focus on clinical trials to improve CIBD, perhaps because so many resources have been devoted to the effort to treat CIAS, but lack of appreciation of the severity of CIBD and its importance as a determinant of functional outcome in BPD may be the most important factors.

In a recent study of CIBD, using the MATRICS Consensus Cognitive Battery (MCCB), impairment was found in both treatment resistant BP I and II depressed inpatients within all MCCB domains [4]. The greatest impairment was evident in speed of processing, declarative memory and attention. The impairment was numerically greater in BP I than BP II patients but the difference was not significant. Compared to normal controls, the deficits, in BP 1 patients, in speed of processing was 1.2SD, in attention, 1.0 SD, and in verbal learning, 1.8 SD. The least affected domain was visual learning, with a mean deficit of 0.8SD compared to normal controls. The mean composite score deficit was 1.25 SD. Medication for BPD, particularly mood stabilizers, may adversely affect some domains of cognition in

BPD [7]. However, antidepressant medications have not been found to affect the severity of cognitive impairment in major depression or BPD [8].

#### 2.1.2 Preclinical Rationale for Studying JNJ-18038683 to treat CIBD and CIAS

Serotonin (5-HT)7 receptors are one of 14 5-HT receptors. This Gs-protein coupled receptor is widely distributed in brain, with high density in the thalamus, hypothalamus, hippocampus, suprachiasmatic nucleus, amygdala and septum, with lower levels in the cerebral cortex. The HTR7, is positively coupled to adenylate cyclase (as are the dopamine (DA) D1, 5-HT4 and 5-HT6 receptors), and has aroused considerable interest as a target for drugs to treat depression, as well as some for cognitive impairment and psychosis [9-11]. For example, there has been considerable interest in 5-HT7 antagonists as stand-alone antidepressants [10, 12, 13] or as contributor to multireceptor antidepressant drugs [14-16]. JNJ 18038683 and other selective 5-HT7 receptor antagonists have been reported to be effective antidepressants in a variety of animal models, including tail suspension [13]. JNJ-18038683 potentiated the ability of a sub-effective dose of the SSRI citalogram to increase extracellular levels of 5-HT in rat cortex. JNJ-18038683 had no effect by itself on 5-HT efflux in a microdialysis study. In a failed clinical trial, JNJ-18038683 did not differentiate from placebo, but the active comparator also did not differentiate, possibly because of a high placebo response rate. Importantly, no safety concerns emerged for the compound [13].

Of key relevance to this proposal, 5-HT7 receptor selective drugs have been shown to be active in animal models of psychosis, learning, and memory [10]. 5-HT7 receptor blockade has been postulated to be a key component of the cognitive enhancement due to atypical APDs, e.g. amisulpride, clozapine, lurasidone, and risperidone, which are potent 5-HT7 antagonists [17-19] and as a stand-alone cognitive enhancer [20]. We will report key additional evidence in the Preliminary Studies section. With regard to animal models of antipsychotic activity, the selective 5-HT7 antagonist, SB-258471, prevented the disruption of prepulse inhibition (PPI) in phencyclidine (PCP)-but not amphetamine-treated rats, indicating positive influence on the glutamate, but not DA, component of PPI, a model of the sensory gating deficit in BPD and schizophrenia which has bearing upon antipsychotic activity and attention, a key component of CIBD [9]. However, the selective, 5-HT7 antagonist SB269970 [21] was able to reverse the effect of amphetamine to disrupt PPI in C57BL/6 mice [9]. It has been reported that SB-269970 significantly reversed the NMDA receptor antagonist dizocilpline (MK-801)-induced deficits in the delayed non-matching to position task, a measure of working memory, but augmented the deficit induced by low dose scopolamine, a muscarinic antagonist [22]. These authors also showed that SB-269970 normalized MK-801-induced glutamate but not DA efflux in the prefrontal cortex. SB269970 improved reference memory in a radial arm maze [9, 12] and a PCPinduced reversal learning deficit in rats [23]. SB-656104-A, another 5-HT7

[figure not shown]
antagonist, improved learning and memory deficits induced by an NMDAR antagonist, in the rat passive avoidance test alone and with a subeffective dose of lurasidone [24]. Sarkisyan and Hedlund [25] reported a deficit in spatial memory in a novel location test in 5-HT7 knock out mice and mice treated with SB-269970. However, we have found no deficit in novel location in HTR7 knock out mice. In a recent publication, Andressen et al There is some conflicting evidence about the role of 5-HT7 antagonism in cognition. 5-HT7 agonism has been suggested to be an effective target for improvement of cognitive impairment in aging mice and in an Alzheimer's mouse model, as the 5-HT7 agonist AS19 enhanced memory formation in an autoshaping task, an effect blocked by SB269970 [26]. Gasbarri et al [27] suggested that the role of the 5-HT7 receptor in cognition will vary depending upon the task and brain regions involved. Eriksson et al [28] suggested that 5-HT7 receptor blockade can intensify impairments in emotional memory that are induced by 5-HT1A receptor stimulation.

[figure not shown]
#### 2.1.3 Preclinical Evidence:

[figure not shown]
The predominant strategy to develop pharmacologic treatments for CIAS and by extension, CIBD, relies upon ameliorating cognitive impairment induced in rodent models which have some relation to the psychotic spectrum disorders, especially drug- or transgenic-induced abnormalities in cognition. Evidence from animal models suggests that serotonin (5-HT)7 receptor(R) antagonism is a promising target to treat CIBD and CIAS. We have extensively studied SB-269970, the protypical 5-HT7 selective antagonist, in the sub-chronic (sc) phencyclidine (PCP) rat and mouse models of CIAS. PCP, an NMDAR antagonist, is widely studied for this purpose because of the extensive evidence that abnormalities in glutamate and GABA neurotransmission in cortex and hippocampus may be the prime cause of CIAS. Acute or scPCP produces a wide range of documented deficits in NMDAR and GABA neurotransmission. We recently reported that SB269970 (0.1-1 mg/kg) dose-dependently reversed scPCP-induced novel object recognition (NOR) deficits in rats [17]. NOR is a model of human declarative memory. We have replicated these results in mice treated with PCP or ketamine for 7 days and washed out 7 days or longer (Figure 1). SB-269970 can also reverse PCP-induced deficits in novel location detection. Our data contrasts with results from the Hedlund lab. In addition, we reported that the ability of two atypical antipsychotic drugs (APDs), lurasidone (0.1 mg/kg) and amisulpride (3 mg/kg), to reverse the NOR deficit was blocked by co-treatment with the 5-HT7 receptor agonist, AS19, (5-10 mg/kg). None of these compounds affect NOR in naive rats. There is also extensive evidence supporting the cognitive benefits from 5-HT7 receptor blockade from other labs, e.g. restoration of reversal learning in PCP-treated rats. Furthermore, we have been breeding 5-HT7 knock out mice for a year and now have many studies with these mice which replicate the results with SB-269970, including prevention of the NOR deficit produced by acute or sub-chronic PCP (Figure 2). In addition, the 5-HT7 knockout mice, from adolescence to adulthood,

show superior duration of memory for NOR compared to wild type mice (Supplemental Figure 1). Figures referenced below include the discrimination index of the NOR experiments, which quantifies the animal's ability to recognize and explore the novel object more than the familiar.

Figure 1: Effect of SB269970 to restore NOR at 24 and 48 hrs after Acquisition

[figure not shown]

- Vehicle+vehicle
   PCP+vehicle
   PCP+vehicle
   PCP+SB269970(0.3 mg/kg): sub-effective dose
   PCP+SB269970(0.5 mg/kg): partially effective dose
   PCP+SB269970(1 mg/kg): effective dose
   PCP+SB269970(1 mg/kg): effective dose 48 hr ITI
- \*P<0.05: significant reduction in DI compared to vehicle #####P<0.01 P<0.001: significant increase in DI compared to PCP

[figure not shown]
Our lab has also conducted studies with JNJ-18038683 which indicate that it is as effective as SB269970 to restore NOR in scPCP-treated mice (Figure 3).

#### Additional Evidence for Pro-cognitive effects of JNJ-18038683 on Executive Function:

Reversal learning: See Abdul-Monim et al., and Brigman et al., [29, 30] for detailed methodology. Apart from the declarative memory deficits, there is a range of cognitive deficits in BPD and schizophrenia, including impaired executive functioning [31], which can be assessed by operant reversal learning tasks in rodents [32]. We found that both JNJ-18038683 and SB269970 (4 mg/kg) were able to reverse sub-chronic PCP induced decrease in percentage correct responding in the reversal phase of the task (Figure 4).

Figure 4: Effect of 5-HT7 antagonists on executive function in PCP treated animals Figure 3: Acute reversal of sub-chronic PCP with JNJ-18038683: Determination of effective and sub-effective doses (1.0 mg/kg and 0.3 mg/kg, respectively)

- 1. Vehicle+vehicle
- 2. PCP+vehicle
  3. PCP+SB269970 (0.5 mg/kg) sub-effective dose
  4. PCP+SB269970 (4 mg/kg) effective dose
  5. PCP+JNJ18038683(1 mg/kg) sub-effective dose
- 6. PCP+JNJ18038683 (4 mg/kg)-Effective dose
- \*P<0.05: significant reduction in percentage correct responding compared to vehicle group; #P<0.5; ##0.01: significant increase in percentage correct responding compared to PCP

#### 2.2 Rationale for Randomized Controlled Trial of JNJ-18038683 on Cognition and Residual Depressive Symptoms in Bipolar Disorder

Based on the pre-clinical, pro-cognitive effects of 5-HT7 antagonism in our laboratory, along with the reported pre-clinical antidepressant effects of JNJ-18038683, we propose to conduct a randomized, placebo-controlled parallel, design study to assess the effects of JNJ-18038683 on multiple domains of cognition and mood symptoms. Since our preclinical studies show that 5-HT7 receptor blockade is highly effective in improving declarative memory in rodents. the declarative memory measures will be the primary outcome measures. As previously discussed Andressen et. al [39] noted differential functional selectivity of the 5-HT7 receptor, suggesting that the effects of atypical APDs with known 5-HT7 antagonism, such as lurasidone, ziprasidone and risperidone, are modulated via different HTR7 subunits than JNJ1083868. In light of this new information, we proposed to allow some individuals currently prescribed treatment with atypical APDs with 5-HT7 antagonism to be eligible for screening and randomization.

Due to the effect of JNJ-18038683 on depressive symptoms in preclinical paradigms [12], we will investigate the following in the clinical trial the potential antidepressant effect of JNJ-18038683 on patients with baseline MADRS score between 8 and 20.

#### 3.0 Inclusion and Exclusion Criteria

All patients will meet criteria for DSM-V diagnosis of Bipolar I or Bipolar II disorder. At the time of enrollment, patients will be relatively stable, and may be in a mild-moderate depressed state. 60 patients will be enrolled, and randomized in a 1:1 ratio to one dose of JNJ-18038683 or placebo. Randomization will be stratified by the presence / absence of atypical APDs with 5-HT7 antagonism so that there is a balance in the assignment of active treatment and placebo in individuals who are, and are not, receiving atypical APDs with 5-HT7 antagonism. The percentage of those enrolled that are prescribed these atypical APDs will be 35% of the overall enrollment.

Individuals must meet all of the inclusion and exclusion criteria to be registered to the study. Study treatment may not begin until a subject is registered.

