## 11.0 Data and Specimen Management

#### 11.1 Data Analysis Plan

The primary analysis will be a mixed model repeated measures ANCOVA adjusting for baseline differences in dependent measures, sex and race. Missing data will be imputed by MMRM. We would also examine some variables categorically.

Assumptions for the power analysis included random assignment into one group receiving placebo and one JNJ-18038683. The cognitive battery, as the primary instrument, will be collected at baseline and at end point (8 weeks). Using repeated measure ANCOVA, the time average difference in the response variable will be compared between groups to detect treatment difference. Based on Javitt et al, 2012, we assume the mean baseline verbal learning score will be 36.2, SD 9.4 for both groups. We are assuming the placebo group will show no improvement while the treatment group will improve a mean of 5 points, a medium effect. We assume the correlation coefficient of repeated observation to be 0.5 and the covariance structure to be compound symmetry. The power calculation was conducted with alpha level of 0.05 using one-sided and two-sided tests. Full results are available upon request. With a one sided test, 33 individuals per group are required assuming 5 points improvement of the treatment group compared to the placebo for the desired power of 80% with alpha level of 0.05. We plan to recruit 36 per group to account for drop outs. In the two sided test the sample size per group is 42.

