#### 22.0 Local Number of Individuals

After screening for eligibility and providing written informed consent, 60 stable outpatients, who may have mild-moderate depressive symptoms, will be randomized to receive adjunctive treatment with either JNJ-18038683 or placebo.

We propose to study a total of 60 randomized participants, 30 receiving JNJ-18038683 and 30 randomized to placebo.

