Data Analysis Plan for Northwestern- Janssen R&D Collaboration Study

Protocol Title: Testing the ability of JNJ-18038683, a selective serotonin (5-HT)7 antagonist, to

improve cognition and reduce residual depressive symptoms in stable bipolar patients

Protocol Identifier Number: 18038683BCD2001

Northwestern University IRB Number: STU00200919-MOD0042

Version: 1.13

Date: 08.04.2021

Goals:

The goals of this study are to evaluate the efficacy of JNJ-18038683 in an 8-week trial to ameliorate the cognitive deficit and reduce residual depressive symptoms in 60 stable bipolar outpatients receiving treatment for depression. JNJ-18038683 will be studied and compared with placebo as adjunctive treatment to standard pharmacologic treatment for bipolar disorder. Sixty patients will be enrolled and randomized with a 1:1 ratio to one dose of JNJ-18038683 or placebo providing 30 subjects for each treatment arm. The initial intention was to follow stratified randomization based on the presence/absence of atypical APDs with 5-HT7 antagonism so that there is a balance in the assignment of active treatment and placebo in individuals who are and are not, receiving atypical APDs with 5-HT7 antagonism. However, due to recruitment difficulties, the stratified randomization method was not able to be followed as anticipated and was amended.

Assessments and Events:

Demographics, medical history, physical examination, serum pregnancy test, urine drug test, SCID-I diagnosis, and screening neurocognitive assessments will be done only during the screening visit. Urine pregnancy testing is performed at the baseline visit.

Table 1: Assessments completed during the screening visit only

Event /Assessment	Screen
Medical History & Demographics	X
Physical Examination	X
Serum Pregnancy Test	X
Urine Drug Screen	X
Inclusion/Exclusion Criteria	X
SCID-I	X
Screening neurocognitive assessments	X

Neurocognitive battery will be the primary measure of interest and evaluated at baseline and 8 weeks. The clinical global severity scores (CGI-BP), Young Mania Rating (YMRS), Scale for Tardive Dyskinesia (AIMS), Montgomery Asberg Depression Rating Scale (MADRS), Electrocardiogram and Clinical Safety Laboratory Tests will be collected at screening or baseline, and at 4 and 8 weeks. A measure of functional ability (SLOF) also will be assessed at baseline and 8 weeks. The schedule of these assessments is listed in table 2.

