The primary outcome measure for this study is verbal fluency performance as assessed with the Rey Auditory Verbal Learning Test, Rey Verbal Learning Test – Recognition Form, Verbal Fluency Test "Letterforms", and Animal Naming Test. The 8-week evaluation of verbal fluency after randomization is the primary outcome measure. Since the main interest is to measure the treatment effect for verbal fluency improvement from baseline and there is only one follow-up time point for the primary outcome variable, an ANCOVA model will be best suited for this study to compare the treatment effect using baseline value as a covariate. Alternatively, an ANOVA model will be used to compare the percent improvement and changes in the verbal fluency scores across treatment groups. Also, we plan to compare the treatment effect on verbal fluency performance over time using a mixed model. The missing evaluations will be imputed with the last value carried forward method, while model fit statistics will be used to estimate the appropriate covariance structure for this model.

There is both preclinical and clinical evidence that age has an important influence on 5-HT7 receptor function, which is the target of JNJ-18038683. Capacity to respond to JNJ-18038683 may decline with age. Thus, we predict the age of the subject will be related to the extent of improvement in verbal fluency and other measurements in the cognition battery. The relationship of age and percent improvement and the direct change of verbal fluency from baseline to 8 weeks in each treatment arm will be assessed using correlation analysis. The age variable will be used as a continuous variable in the analysis. If the distribution of the age variable is skewed, then age groups will be formed appropriately. In the above described ANCOVA and repeated measures models, age will be use as a covariate to assess the treatment effect. Graphical methods will be used to check for any inflection points of improvement of verbal fluency score in the treatment group compared to placebo. In the treatment group, better improvement is expected in younger patients compared to older patients. This relationship is not expected in placebo-treated patients. Additionally, with the above-mentioned models, the effect of covariates, MADRS total score, YMRS and Clinical Global Severity score on cognition will be examined because baseline mania or depression severity may influence performance on cognitive testing.

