Secondary analyses related to efficacy:

The secondary analyses regarding change in verbal fluency test scores will include identification of patients in each arm who improved in verbal fluency scores. The analysis plan includes exploring the effect of concomitant meds, gender or race that might contribute to treatment response. For this purpose, improvement in verbal fluency can be grouped as a dichotomous response and used as a dependent variable in a logistic regression model. The usual method of grouping will be improvement of ≥0.5 SD from the baseline scores. Using this model, the odds of improvement in verbal fluency can be compared in the active treatment group against the placebo group. In this model, the variables, age, gender, lab values and presence/absence of concomitant meds, baseline MADRS total score, YMRS and Clinical Global Severity score mania or depression severity may influence performance on cognitive testing and will be tested as potential covariates using one or few covariates at a time due to sample size restrictions.

Additional secondary analyses will study the effect of treatment group on other cognitive and behavioral measures including: 1) Digital Symbol Task, 2) Brown-Peterson Consonant Trigram Memory Task, 3) WISC-III Mazes; 4) Wisconsin Card Sorting Test; 5) MADRS total score,6) YMRS, and 7) Clinical Global Severity score using a mixed model repeated measure ANCOVA as described above. If indicated, variables such as age, gender, concomitant meds, will be examined, as will be done for the primary outcome measure.

Adverse Events:

A tabular summary of all anticipated and unanticipated serious or non-serious adverse events will be presented, including drop-outs due to any side effects or safety reasons. For each serious or other adverse events, the summary includes the adverse event term, affected organ system, number of participants at risk, and number of participants affected, by the study arm or comparison group. Using appropriate parametric or non-parametric methods, each type of adverse event will be compared between groups. All adverse events, e.g. development of suicidal ideation or behaviors or switch to mania/hypomania, will be examined thoroughly for impact on primary and secondary outcome measures. We will assess group differences, excluding subjects without these two side effects.

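### Use of 5-HT7-antagonist antipsychotics, a factor the protocol chose to stratify by, is handled inconsistently across the documents and is not pre-specified in either primary model, so imbalance or a smaller effect in users could go unseen

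*Protocol*

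**What the plan says.** Protocol section 3.0 stratifies randomisation by whether a patient takes an atypical antipsychotic with 5-HT7 antagonism, and gives balance between arms as the reason. It adds: "The percentage of those enrolled that are prescribed these atypical APDs will be 35% of the overall enrollment". Section 22.0 sets the size: "We propose to study a total of 60 randomized participants, 30 receiving JNJ-18038683 and 30 randomized to placebo". Together these plan for 21 users among 60. Inclusion criterion 11 attaches dose conditions to risperidone, lurasidone and ziprasidone, which presupposes that patients on them can enter.

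Other places do not fit:

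- Protocol section 9.0 rules out any antipsychotic that is a 5-HT7 antagonist.
- Protocol sections 9.0 and 9.2 name antidepressant use as the stratification factor.
- The SAP, under Goals, says that because of recruitment difficulties "the stratified randomization method was not able to be followed as anticipated and was amended". It does not say what replaced it.

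On the analysis, protocol section 11.1 adjusts for baseline, sex and race. The SAP's primary analysis says "an ANCOVA model will be best suited for this study to compare the treatment effect using baseline value as a covariate", adds age, and will examine MADRS, YMRS and clinical global severity. Neither names antipsychotic use, an interaction with it, or an estimate by it. The SAP's secondary section states: "The analysis plan includes exploring the effect of concomitant meds, gender or race that might contribute to treatment response". The vehicle there is a logistic model of a dichotomised improvement score. A later sentence says that concomitant medication will be looked at for the other measures if indicated, as for the primary outcome.

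**The concern.** The protocol's own background gives reasons to think this factor could change the drug's effect. Section 2.1.2 says that 5-HT7 "receptor blockade has been postulated to be a key component of the cognitive enhancement due to atypical APDs, e.g. amisulpride, clozapine, lurasidone, and risperidone". Section 2.1.3 reports that a 5-HT7 agonist blocked lurasidone's reversal of a memory deficit in rats. If the receptor is already partly blocked in users, adding the study drug may do less for them.

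Two things are at stake. First, balance: the protocol wanted the arms balanced on this factor, the planned stratification did not hold, and the primary model does not make up for it. Second, interpretation: if users respond less, the pooled difference is smaller than the difference in non-users, and nothing pre-specified would show it. A null pooled result would then leave open whether the drug is inactive or the target was already occupied in part of the sample.

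**Working it through.** **Inputs.** From protocol section 11.1: the effect, stated as "We are assuming the placebo group will show no improvement while the treatment group will improve a mean of 5 points, a medium effect"; a verbal learning SD of 9.4 in each arm; correlation 0.5 with compound symmetry, two time points, alpha 0.05. From sections 3.0 and 22.0: 35% users, 30 per arm. From no document, hence assumed and varied: f, the fraction of the 5-point effect that users keep.

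**1. Reproduce the plan's figures.** The SD of a two-point average is 9.4 × √((1 + 0.5)/2) = 8.141. This gives 33 per group one-sided (power 0.802) and 42 two-sided, as stated. A Week 8 ANCOVA with correlation 0.5 has the same residual SD, 9.4 × √(1 − 0.25) = 8.141, so the figures carry over to the SAP's model if its outcome behaves like the verbal learning score in the power calculation. The plan assumes one common effect, with no allowance for users.

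**2. Pooled effect and power at 30 per arm.** Standard error = 8.141 × √(2/30) = 2.102. Pooled effect = 5 × (0.65 + 0.35f). Power is the normal probability below (effect/2.102 − 1.645) one-sided, with 1.96 for two-sided.

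| f | Pooled effect | One-sided power | Two-sided power |
|---|---|---|---|
| 1 | 5.00 | 77% | 66% |
| 0.75 | 4.56 | 70% | 58% |
| 0.5 | 4.13 | 62% | 50% |
| 0 | 3.25 | 46% | 34% |

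The first row lies below 80% because 30 per arm is fewer than the stated 33. That is a separate matter.

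**3. If the user share is not 35%.** With share p, the pooled effect is 5 × (1 − p(1 − f)). If no users entered, it is 5 and nothing is lost. At an assumed p = 20% and f = 0, it is 4.0; 4.0/2.102 − 1.645 = 0.258, so one-sided power is 60%.

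**4. Chance imbalance.** If 21 users among 60 are allocated 30:30 without regard to use, the number in one arm is hypergeometric. The probability of 8 or fewer, or 13 or more, is 0.279; of a 14:7 split or worse, 0.103.

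**5. What a 13:8 split could do.** The user share then differs by 5/30 between arms. If users differ from non-users at Week 8 by an assumed 0.2 to 0.5 residual SD after baseline adjustment, the treatment estimate shifts by 8.141 × (5/30) × 0.2 = 0.3 to 8.141 × (5/30) × 0.5 = 0.7 points.

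**6. Precision of estimates by use.** With 39 non-users (19.5 per arm) the 95% half-width is 1.96 × 8.141 × √(2/19.5) = 5.1 points. With 21 users (10.5 per arm) it is 1.96 × 8.141 × √(2/10.5) = 7.0. The interaction has standard error 8.141 × √(2/19.5 + 2/10.5) = 4.41, so a 5-point interaction has about 30% power one-sided and 20% two-sided.

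**The case against.** The case against is substantial in five respects.

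- **The pooled comparison answers the stated question.** Section 1.0 asks about efficacy as an addition to standard treatment. An average over permitted background therapy is that effect. This stands.
- **Dilution is conjecture.** Section 2.2 argues that these antipsychotics act through different receptor subunits from the study drug, and admits users for that reason. No document gives f, and at f = 1 nothing is lost. This stands as far as size goes. It does not settle the matter: the argument is put as a suggestion, and the title of the paper cited for it (reference 39) names clozapine and olanzapine, not the lurasidone, ziprasidone and risperidone under discussion. Section 2.1.2 also reports a 5-HT7 antagonist improving memory deficits together with a subeffective dose of lurasidone, so an interaction could run either way.
- **The SAP does not ignore concomitant medication.** A reader might infer that the factor can enter only through the secondary logistic model. The SAP's later sentence links such an examination to the primary outcome as well. That wording, however, names no drug class, model term or interaction, and leaves the choice until the data are seen.
- **The 35% is uncertain.** Section 9.0 conflicts with it, and the SAP reports recruitment difficulties. A reader might also infer that stratification was abandoned altogether; the SAP says only that it was amended. The 28% in step 4 is therefore conditional on 21 users and no stratification on use.
- **The effect of imbalance may be small.** Step 5 gives 0.3 to 0.7 points against an assumed effect of 5, for assumed differences between users and non-users.

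None of this is a reason to leave out of the primary model a factor that the protocol set out to balance.

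**Conclusion.** The point holds as one of pre-specification and consistency. The documents contradict each other on whether users of 5-HT7-antagonist antipsychotics may enter and on which factor was stratified. Balance on antipsychotic use is not assured by design or restored by either primary model, and a different effect in users would not be seen.

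The size is a range. With 35% users and 30 per arm, one-sided power runs from 77% (users keep the full effect) through 70% and 62% to 46% (users keep none). It rests on the protocol's SD, correlation and 5-point effect, on equal user shares in the arms, and on an f that the documents do not supply.

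Two stronger readings are not supported. A reader might infer that the pooled estimate is wrong and that the conclusion on mechanism should be drawn from non-users. But about 39 non-users give 61% power one-sided (48% two-sided) for 5 points. The pooled test does at least as well once 0.65 + 0.35f reaches √(19.5/30) = 0.806, that is, f of about 0.45 or more. A null result in non-users would be no easier to read. Nor do the documents call the factor prognostic; section 3.0 gives balance as its only reason for stratifying.

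**What to change.** 1. Reconcile protocol sections 3.0, 9.0 and 9.2 and the SAP's Goals: whether users could enter, which factor was stratified and from when, and what the amended scheme was.
2. In the SAP, add baseline use of a 5-HT7-antagonist antipsychotic (yes/no, from a named drug list) as a covariate in the primary Week 8 ANCOVA.
3. Report the number of users per arm.
4. Pre-specify the treatment-by-use interaction and the treatment difference in users and in non-users, each with a confidence interval, labelled as supportive. The covariate deals with imbalance; only these estimates can show a different effect in users.
5. State that the pooled estimate remains the primary conclusion.

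The cost is SAP wording, one table and one degree of freedom in the primary model. Concomitant medication is already recorded at screening and baseline. The by-use estimates will be imprecise (step 6), so the SAP should say beforehand that a non-significant interaction is not evidence of equal effects.
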